## **Children and Women**

No children will be recruited for this study. VA requires a waiver for a research on children and currently VASDHS does not offer a pediatric service. Female subjects who meet the study inclusion and exclusion criteria will be recruited. Female Subjects at childbearing age will be required to have a urine pregnancy test prior to the enrollment.

## **Follow Up Appointments in response to COVID-19:**

In response to COVID-19, we are requesting that follow up visits be conducted via telephone, Doximity, and/or email. Questionnaires (Headache Impact Test, Neurobehavioral Symptom Inventory, Brief Pain Inventory, SF-36, and Modified Fatigue Impact Scale) will be emailed to subjects to view and a phone or Doximity call will be conducted where subjects can verbally respond to the questionnaires emailed and the Hamilton Rating Scale for Depression and Hopkins Verbal Learning Test will be administered. This will be applicable for subjects currently in the follow up phase and for use only during the COVID-19 response.

## **Protocol Changes in Response to COVID-19**

In response to the COVID-19 pandemic, we are proposing changes in study design with increased safety measures based on the 12-step model listed in "Guidelines for TMS/tES Clinical Services and Research through the COVID-19 Pandemic" by Ehktiari et al. to reestablish research and open enrollment while mitigating potential risks associated with the virus. The changes to the protocol will

consist of conducting baseline and follow up assessment visits over phone or video call. Some assessments will be removed due to the inability to conduct them over phone/video call. Consenting and screening will also be conducted over the phone/video call. In addition, stringent safety and sanitization measures will be implemented to reduce risk that include limiting staff presence, PPE for subjects and staff, COVID-19 screening, and increased and frequent sanitization of equipment.

## **STUDY DESIGN - COVID-19**

The original study design was conducted according to the following schedule where all visits were conducted On-site:

Visit 1: Consent and Screening Visit;

Visit 2: Pre-treatment Assessments and MRI Scan;

Visits 3-12: Study Treatments;

Visit 13: Post-treatment 1-week assessment and MRI Scan;

Visit 14: Post-treatment 2-week assessment;

Visit 15: Post-treatment 4-week assessment;

Visit 16: Post-treatment 8-week assessment;

Visit 17: Post-treatment 12 -week assessment

To reduce physical interaction and exposure risk, a new study timeline will convert all visits that do not necessitate an on-site visit (i.e. consenting, screening, and assessments) to remote telehealth visit. In addition, visits 2 and 13 will be broken up to 2 visits in which assessments will conducted remotely and the MRI conducted on site. These on-site visits will not be implemented until written approval from the ACOS/R&D that on-site visits may be resumed. The visits will be revised as the following with visits either conducted through telehealth (TH) or onsite (OS):

1: Consent/Screen - TH;

2a: Pre-treatment (TX) Assessments - TH;

2b: Pre-TX MRI - OS;

3-12: Induction Treatments - OS;

13a: Post-TX 1-week assessment - TH;

13b: Post-TX MRI - OS;

14: Post-TX 2-week assessment - TH;

15: Post-TX 4-week assessment - TH;

16: Post-TX 8-week assessment - TH;

17: Post-TX 12-week assessment - TH;

The following table summarizes the visits, location of each visit, timeline, and procedures to be conducted at each visit:

Visit	Visit Name	Location	Timeline	Procedures
1	Consent /Screen	Telehealth	Day 0	Consent/HIPAA Form Screen for eligibility
2a	Pre-TX Assessments	Telehealth	Within 7 days of consent	Assessments and Questionnaires
2b	Pre-TX MRI	On-Site	Within 1-2 days of V2a	Anatomical, DTI, Resting and HP fMRI Physical exam for screening
3-12	Induction Treatments	On-Site	First treatment to begin 7-10 days of V2b	TMS Treatments (>24 and <72 hours apart)
13a	Post-TX 1 Week Assessments	Telehealth	Within 6-8 days of V11	Assessments and Questionnaires
13b	Post-TX MRI	On-Site	Within 6-8 days of V11	Anatomical, DTI, Resting and HP fMRI
14	Post-TX 2 Week Assessments	Telehealth	Within 28-31 days of V11	Assessments and Questionnaires
15	Post-TX 4 Week Assessments	Telehealth	Within 28-31 days of V11	Assessments and Questionnaires

16	Post-TX 8 Week Assessments	Telehealth	Within 56-62 days of V11	Assessments and Questionnaires
17	Post-TX 12 Week Assessments	Telehealth	Within 84-93 days of V11	Assessments and Questionnaires

Table 1: Summary of Study Design in Response to COVID-19

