#### Research Design:

A total of 200 will be consented and 128 (64 per group, accounted for 36% dropout rate) patients will be randomized to be stratified based on their injury mechanisms (blast, non-blast) and headache severities (mild, moderate, severe) and enrolled over 6 years from VASDHS, and Naval Medical Center San Diego (MNCS). Patients meeting study enrollment criteria will be randomized into one of the two study groups (A&B) based on their mechanisms of injury, gender, severity of headache, and past failed therapies for their headache. The overall study duration for each subject is about 14 weeks developed into three phases according to the following schedule:

- 1) PRE-TREATMENT PHASE (weeks 1-2) consists of Visit 1 (Screening Visit) and Visit 2 (Pre-treatment Assessments);
- 2) TREATMENT PHASE (week 3-4) consists of Visits 3-12 (Neuronavigation guided rTMS consisting of 10 weekday treatments at  $>24$  and  $< 72$  hours apart, weekends excluded, maximum 5 weeks for treatment completion) rTMS will take place in Building 23 Room 105 at the VASDHS; and

3) POST-TREATMENT PHASE (week 5-14) consists of two initial weekly visits (Visits 13&14) and two additional biweekly visits (Visits 15&16) and one monthly visit (Visit 17).

Brain anatomical and functional MRI will be performed within 72 hours after Visits 2 and 13. Subjects will be required to fill out headache diary between assessment visits. Headache assessments along with quality of life, mood and functions assessments will be carried out at Visits 1,2, and 13--17. This frequency of treatment and duration of follow-up is in line with recently published rTMS articles related to TBI, headache and pain, and also in accordance with the 3-month post treatment initiation follow-up guideline /recommendation [32; 55; 80].

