## **III). Determination of resting motor threshold**

This assessment will be conducted at the first (Visit 3) and the last (Visit 12) treatment session. A constant suprathreshold stimulus intensity will be applied via a figure-of-eight coil, which will be moved under the guidance of TMS Neuronavigation over the left motor cortex (Brodmann Area 4). Once the optimal location is visually identified, a single pulse TMS will be delivered to that location starting at the suprathreshold intensity and decreasing in steps of 2 % of the stimulator output. The resting motor threshold (RMT) will be defined as the minimal intensity required to elicit motor evoked potentials of 50 V peak to peak amplitude in five out of 10 consecutive trials [30]. The location of the cortex used for the establishment of the RMT will be marked on the neuronavigational software and used for subsequent treatments. The distance between the center of the probe and the target site will be recorded as well.

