increased power to detect effects and precision for the estimation of the effect sizes without requiring increased sample size, and provide the study with a uniform method of data analysis for all hypotheses that include multiple measurements from the same subjects. The mixed effects model method provides an estimate of the individual variability around the population trend, the variability of the individual intercepts (baseline values) and slopes (changes across time), and the correlation between them. A fully saturated treatment by time model will be utilized for inference. Co-variance structure will be chosen based on Akaike's Information Criterion (AIC). This allows for any group level effects to be incorporated into the model. Denominator degrees of freedom will be calculated using the Kenward-Roger small sample correction. Analyses will be conducted within and across nested levels of the study design; this will involve within-subject analyses (comparison of occasions of measurement nested within an individual), as well as between-subject analyses (comparison of two groups). In addition, any treatment group comparison can be adjusted for subject-specific characteristics and adjustments for changes in these characteristics over the course of the study, and incorporated into the single-subject analyses. Based on investigators' experience with previously completed studies, we expect a dropout rate of 10 to 20% throughout the study. All analyses will be two-tailed, where applicable, with  $\alpha = .05$ . Correction for family-wise Type I error rates will be made using the Westfall-Young randomization maxT procedure, which adjusts p-values for significance while taking into account the correlation of the outcomes [70]. In this way we can control for an overall family-wise error rate of .05 while achieving more power than Bonferroni adjustments.

**Hypothesis #2:** Active rTMS at LMC provides significantly more improvement in quality of life, mood and functions than sham LMC stimulations.

Independent Variables: Treatment Groups with two levels (Groups A & B), Visits with 8 levels: pre-treatment (Visit 2), treatment (Visits 7 & 12), and Post-treatment (Visits 13, 14, 15, 16, 17).

Dependent Variables: Attention (CPT II), Memory (Hopkins Verbal Learning Test) Execute function (Trail Making Test A and B, and Stroop Test), Hamilton Depression Scale, SF-36 and BPI.

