## Section 20 - Compensation for Participation

### 20) Provide all details and justifications of the compensation plan. See ? for detailed requirements.

To compensate the study subjects for their travel expense and time spent with the study activities, and to maximize subject retention, each subject will be reimbursed \$30 for the screening visit (Visit 1) and each of the 10 treatment visits (Visits 3-12). For all the other visits, each subject will receive \$50 for each of the 6 assessment visits and 2 MRI visits. For all the visits, we budget a total \$730 compensation fee for each subject. The payments will be made directly to their bank account using electronic funds transfer.

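### Table 1 of the COVID-19 schedule gives the 2-week visit (V14) the 4-week window, and counts all post-treatment visits from V11, the ninth of ten sessions, instead of V12

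*Combined protocol and SAP*

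**What the plan says.** The ten sessions are Visits 3 to 12. Section 20 pays for "each of the 10 treatment visits (Visits 3-12", and the section on the resting motor threshold identifies Visit 12 as the end of the course: "This assessment will be conducted at the first (Visit 3) and the last (Visit 12) treatment session". The independent variables for Hypothesis #2 class Visit 12 as treatment and the next five visits as follow-up: "treatment (Visits 7 & 12), and Post-treatment (Visits 13, 14, 15, 16, 17".

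Under STUDY DESIGN - COVID-19, the on-site treatments stay at Visits 3-12, and both visit lists keep the 1-, 2-, 4-, 8- and 12-week labels, for example "Visit 14: Post-treatment 2-week assessment". Table 1 then sets the windows:

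- V13a and V13b (1 week): "Within 6-8 days of V11".
- V14 (2 weeks) and V15 (4 weeks), in identical words: "Within 28-31 days of V11".
- V16 (8 weeks) and V17 (12 weeks): 56-62 and 84-93 days, also from V11.

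Section 9, Research Design, describes V13 and V14 as "two initial weekly visits (Visits 13&14", followed by V15 and V16 at two-week spacing and V17 a month later, all within study weeks 5-14. It spaces the sessions more than 24 and less than 72 "hours apart, weekends excluded, maximum 5 weeks for treatment completion".

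**The concern.** This is the text staff would schedule from when enrollment reopened under COVID-19, and no other section supplies a day window that would override it.

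For V14, a 4-week window on a 2-week visit means that patients on this schedule have no assessment at 2 weeks and two at about 4 weeks. V14 and V15 are separate visits in the planned mixed models, so the V14 level would hold data of mixed timing. The primary outcome is also exposed. Section 9 A) averages diary intensity over between-visit periods (sum of scores divided by number of days). If visit dates bound those periods, moving V14 stretches one period and nearly empties the next.

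For the anchor, V13 is the first post-treatment assessment and has the only post-treatment MRI, which serves exploratory aim 1. Counting from the ninth session brings both closer to the end of stimulation than the 1-week label implies.

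**Working it through.** **Inputs.** Sessions at V3-V12 (Research Design; Section 20). Windows from V11 as in Table 1: V13 6-8, V14 28-31, V15 28-31, V16 56-62, V17 84-93 days. Session spacing as in Research Design and Table 1.

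**Which session is V11?** There are 12 - 3 + 1 = 10 sessions, and V11 is number 11 - 3 + 1 = 9. V12 is the tenth and last.

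**Do the windows match the labels, anchor aside?** Dividing by 7: V13 0.86-1.14 weeks, V15 4.0-4.4, V16 8.0-8.9, V17 12.0-13.3. These fit labels of 1, 4, 8 and 12 weeks. V14 gives 4.0-4.4 weeks against a label of 2, so it is wrong whichever session is the anchor.

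**Days after the last session** = (window from V11) - g, where g is the V11-V12 gap in calendar days.

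| g | V13 | V14 and V15 | V16 | V17 |
|---|---|---|---|---|
| 1 | 5-7 | 27-30 | 55-61 | 83-92 |
| 2 | 4-6 | 26-29 | 54-60 | 82-91 |
| 3 | 3-5 | 25-28 | 53-59 | 81-90 |

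On ten consecutive weekdays, g = 1 for a Monday, Wednesday, Thursday or Friday start. A Tuesday start puts V11 on Friday and V12 on Monday, so g = 3. A skipped weekday gives g = 2. Across the three gaps V13 falls 3-7 days, and V14 25-30 days, after the last session. Against day 14, V14 is 25 - 14 = 11 to 30 - 14 = 16 days late.

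**Diary periods** (assuming visit dates bound them; the anchor cancels).

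- V13 to V14: 28 - 8 = 20 to 31 - 6 = 25 days. The labels imply 14 - 7 = 7.
- V14 to V15: 0 to 31 - 28 = 3 days. The labels imply 28 - 14 = 14.

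**After correction,** with all rows counted from V12 and V14 at 13-16 days (an illustrative window; the documents give none): V13 to V14 is 13 - 8 = 5 to 16 - 6 = 10 days, and V14 to V15 is 28 - 16 = 12 to 31 - 13 = 18 days.

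**Later visits against Research Design.** Weekly, weekly, biweekly, biweekly, monthly (taken as 4 weeks) gives 1, 2, 4, 6 and 10 weeks after treatment, which fills the ten weeks 5-14. Table 1 and both visit lists in the COVID-19 section give 8 and 12 weeks for V16 and V17, two weeks later in each case.

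**The case against.** The strongest reply is that these are slips whose intent is obvious. Every label says 2 weeks for V14, Section 20 pays for six separate assessment visits, and a coordinator would notice two differently named visits sharing one window. That is persuasive for V11, where V12 is almost certainly meant. It is weaker for V14: no section states the intended days, so staff must either follow a 4-week window or invent one.

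A second reply is that the V11 shift is trivial. It largely stands. With a 1-day gap, two of the three allowed days for V13 still lie in 6-8; V15-V17 barely move; and the MRI serves an exploratory aim.

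A third is that the gap is uncertain, which is fair. The COVID-19 text on reduced staffing mentions alternating treatment schedules. If that means alternate days, g = 2 would be typical. A Friday-to-Monday gap is about 72 hours, so it needs a slightly earlier Monday start or a lenient reading of the weekend wording, which Table 1 does not repeat. A reader might go further, discount weekend hours altogether and put V13 as early as 1 day after the last session; the text does not say that weekend hours are left out of the 72-hour limit.

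Fourth, daily diary entries exist whatever date V14 falls on, and weekly phone contacts continue. This also stands: headache data around week 2 are not lost, although the V14 assessments at that time would be and the diary averages would be distorted.

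**Conclusion.** The point holds, with V14 as its main part. As printed, the 2-week visit falls about 25-30 days after the last session, 11-16 days late, and shares its window with V15, leaving 0-3 diary days between them. The V11 anchor places the 1-week assessment and MRI about 3-7 days after the last session instead of 6-8 and matters little afterwards.

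This assumes that staff follow the table literally, that g is 1 to 3 calendar days and, for the diary, that visit dates bound the periods; the protocol does not map B1-B6 to visits. It applies only to patients scheduled under Table 1, whose share of the 128 randomized is not given.

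A reader might infer a biased treatment comparison or an inflated type I error. The documents do not support that: both arms use the same table, and patients and assessors are blinded. No power or sample-size figure depends on this point.

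**What to change.** In Table 1:

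- Give V14 a window around day 14, for example 13-16 days.
- Replace V11 with V12 in all six post-treatment rows (V13a, V13b, V14-V17).
- Reconcile V16 and V17 with Research Design. Either 6 and 10 weeks or 8 and 12 weeks can be right, but the same timing should appear in both places.

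For patients already seen under the printed table, analyse V14 data by actual time since the last session, so that a visit at about 4 weeks is not treated as a 2-week value. A separate interval-adjusted sensitivity analysis is not needed, since no between-arm effect is claimed.

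The cost is one table column, a matching edit to the visit timing in Research Design or the COVID-19 section, and use of session and visit dates.

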## **TELEHEALTH VISITS**

All telehealth visits will be conducted through video call through Doximity or VA Video Connect. However, phone calls will be available as back up if there are issues with connectivity or other technical issues preventing video. Video calls will allow the study team to better monitor subjects and create a more personal visit.

### **Consent/Screening – Visit 1**

Consent and screening will take place remotely in which a member of the study team will go over the study details, eligibility, and answer any questions or concerns. Subjects will be given a copy of the consent/HIPAA forms prior to the scheduled visit through MyHealtheVet or mail. Once the consent form/HIPAA has been reviewed and the subject agrees to participate, the subject will be asked to sign the forms (either handwritten or electronically) and return the forms to the study team through either MyHealtheVet or FAX. Subjects will also be screened for the study and COVID-19 over the video call and a physical exam will be conducted by the PI during the first on-site visit (2b). If a subject indicates they have had symptoms of COVID-19, they will be advised to come into the hospital for testing. A negative test (or confirmation that they are no longer positive) will be required before enrollment.

Once a subject is enrolled, an additional phone call will be conducted prior to their baseline assessments to go over the various platforms (Doximity, MyHealtheVet, and VA Video Connect) that will be used for the telehealth visits.

### **Assessment Based Visits – Pre-treatment assessments (V2a), Post-TX 1-week (V13a), Post-TX 2-week (V14), Post-TX 4-week (V15), Post-TX 8-week (V16) and Post-TX 12 week (V17)**

Pre and post-treatment assessments will be conducted over video call, and questionnaires to be completed by subjects will be provided prior to each visit through MyHealtheVet or mailed to the subjects. Subjects will be given the choice to either: 1) complete questionnaires within 24hours of their video appointment and

return them through MyHealtheVet or FAX; or 2) complete them during the video call where subjects will provide their verbal responses and the study coordinator will document the response. The following assessment will have changes on administration:

1. Mechanical Visual Analogue Scale (MVAS) of Headaches, Muscle, and Joint Pain: subjects will rate their pain on the 0-100 MVAS scale at all On-site visits

The following assessments will not be conducted as they require in-person administration:

1. Stroop Test
2. Eye Tracking Assessment
3. Conner's Performance Test II
4. Trail Making Test

These assessments are part of the secondary hypothesis, measuring attention and executive functioning. Though these functions will not be measured, the primary aim of this study is to assess headache and quality of life and assessments related to the primary aim will still be administered.

All other assessments listed in the protocol will be administered with no changes, other than being conducted remotely. Subjects will continue to keep a daily log of their headaches and medication usage throughout the course of the study which will be collected by either sending it through MyHealtheVet or through FAX.

The following table summarizes the assessments/questionnaires administered:

Visit		2	2	3-	1	1	1	1	1
		a	b	12	3	3	4	5	6
					a	b			
Location		T	O	O	S	T	O	T	T
		H	S		H	S	H	H	H
Brief Pain Inventory-Short Form (BPI)	Self-administered		x		x		x	x	x
Neurobehavioral Symptoms Inventory (NSI)	Self-administered		x		x		x	x	x
		x		x	x		x	x	x

Headache Impact Test (HIT-6)	Self-administered					
Short Form Health Survey-36	Self-administered	x	x	x	x	
Hopkins Verbal Learning Test (HVLT)	Study Coordinator	x	x	x	x	
Hamilton Rating Scale for Depression (HRSD)	Study Coordinator	x	x	x	x	
Clinician-Administered PTSD Scale (CAPS-5)	Study Coordinator	x	x	x	x	
Modified Fatigue Impact Scale	Self-administered	x	x	x	x	
MVAS – Sliding Scale	Study Coordinator	x x	x	x	x	

TH: Telehealth; OS: On-site

Table 2: Summary of Assessments in Response to COVID-19

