2) **Neurobehavioral Symptom Inventory (NSI) assessment** which will assess the pattern of headaches and other co-morbid neurological symptoms in Visits 2, 13, 14, 15, 16 & 17 [31; 60]. As a fail-safe assessment for any missing data, subjects will also be asked to rate the average intensity of headache in Visits 2, 13, 14, 15, 16 and 17 for the prior between-visit durations on a 0-100 Mechanical Visual Analogue Scale (M-VAS) [64].

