For hypotheses 1 and 2, where multiple analyses are conducted, correction for family-wise Type I error rates will be made using the Westfall-Young randomization maxTprocedure, which adjusts p-values for significance while taking into account the correlation of the outcomes [76]. In this way, the study can control for an overall family-wise error rate of .05 while achieving more power than Bonferroni adjustments. Using this method of power analysis, the investigators estimated a sample size of 128 (64 per group, accounted for a 20% dropout rate) provides the study with 85% power

to detect a medium effect size (RMASS program provided by Hedeker) [25; 26]. Medium effect sizes were used based on the results included in the above sections. Medium effect size is defined as a between-group difference increasing linearly from 0 at baseline to .5 SD units at the last time point. The minimum power estimation is based on sample size calculation for 10% and 20% attrition, correlations of 0.2, 0.5, and 0.8 between the repeated measures, and for medium and large effect sizes. Data will be analyzed using SPSS version 23, all analyses will be two-tailed, where applicable with  $\alpha = .05$ .

**Hypothesis #1:** Active rTMS at LMC provides significantly more reduction in headache intensity, duration and frequency of exacerbation than sham rTMS.

Independent Variables: Treatment Groups with two levels (Groups A & B), Visits up to 8 (See below). Dependent Variables: Primary outcome: Average daily headache assessments (B1, B2, B3, B4, B5, B6); Secondary outcome: Debilitating Headache Composite Score (B1, B2, B3, B4, B5, B6); M-VAS Scores of headache (Visits 2, 7, 12, 13, 14, 15, 16, 17); HTL-6 and NSI (Visits 2,13,14,15, 16, 17); headache rescue medication usage (Visits 2,13, 14, 15,16, 17). Note, not all variables are collected at all visits.

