### Additional Inclusion Criteria:

1. male or female age between 18 to 65;
2. no prior experience of TMS treatment;
3. average persistent headache intensity more than 30 on the 0-100 mechanical visual analog scale(M-VAS) at the screening visit (visit 1)[64] and average persistent headache intensity score greater than 3/10 on a numerical rating scale (NRS) reported in the headache diary (between visits 1&2);
4. no history of daily persistent headache prior to the MTBI incidence:

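### Under the remote schedule, M-VAS has no stated method at Visit 1, where it is an entry criterion, and its on-site rule conflicts with the ratings required at telehealth Visits 14–17

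*Combined protocol and SAP*

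**What the plan says.** The COVID-19 design converts every visit that does not need attendance to telehealth. Visit 1 is listed as "1: Consent/Screen - TH", and Visits 2a, 13a and 14–17 are telehealth too. The on-site visits are 2b (MRI), 3–12 (treatment) and 13b (MRI).

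Under Assessment Based Visits, the lead-in "The following assessment will have changes on administration" is followed by one item, M-VAS, for which "subjects will rate their pain on the 0-100 MVAS scale at all On-site visits". A separate list names four tests that are dropped; M-VAS is not among them. The section then states: "All other assessments listed in the protocol will be administered with no changes, other than being conducted remotely". Table 2 in the same section has a row labelled "MVAS – Sliding Scale".

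Three other places rely on M-VAS:

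- Additional Inclusion Criteria, item 3 (Section 10) requires "average persistent headache intensity more than 30 on the 0-100 mechanical visual analog scale(M-VAS) at the screening visit (visit 1"), together with a diary NRS average above 3/10 between Visits 1 and 2.
- Section 9, part A (Headache assessment): "As a fail-safe assessment for any missing data, subjects will also be asked to rate the average intensity of headache". The visits are 2 and 13–17, and each rating covers the preceding between-visit period.
- Hypothesis #1 names as a secondary outcome "M-VAS Scores of headache (Visits 2, 7, 12, 13, 14, 15, 16, 17").

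**The concern.** The remote text was written around what can be done over video, and the three uses of M-VAS elsewhere were not updated to match. Two things are at stake.

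The first is eligibility. One of two joint severity criteria is tied to a rating at a visit that is now held by video, with no remote method given.

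The second is long-term follow-up. The trial's stated aim is the long-term effect, and Visits 14–17 are where it is observed. Staff following the sentence as written would take no M-VAS there. That would remove a listed secondary outcome and the designated fail-safe from all remote follow-up after the 1-week visit. Staff following Table 2 might collect some ratings, and the data would then depend on which part of the section was read.

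**Working it through.** No sample size, power or alpha figure bears on this, so the check is a cross-reading and a count.

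**Step 1: visits set side by side.** Mode comes from the COVID-19 study design list; M-VAS use comes from Section 9 part A, Hypothesis #1 and Section 10.

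| Visit | Remote mode | M-VAS needed for | Rated if on-site only |
|---|---|---|---|
| 1 | telehealth | entry criterion | no |
| 2 | 2a telehealth, 2b on-site | fail-safe, secondary outcome | yes, at 2b |
| 7, 12 | on-site | secondary outcome | yes |
| 13 | 13a telehealth, 13b on-site | fail-safe, secondary outcome | yes, at 13b |
| 14, 15, 16, 17 | telehealth | fail-safe, secondary outcome | no |

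**Step 2: count under the on-site-only reading.**
- Fail-safe: six visits (2, 13, 14, 15, 16, 17). Two are kept (2, 13), so 6 − 2 = 4 are lost.
- Secondary outcome: eight occasions (2, 7, 12, 13, 14, 15, 16, 17). Four are kept (2, 7, 12, 13), so 8 − 4 = 4 are lost. These four are all the follow-up after the 1-week visit.

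**Step 3: is on-site only the right reading of the sentence?** M-VAS is the only instrument presented as changed, the change is where it is rated, and all others are then said to continue remotely. The earlier COVID-19 paragraph on follow-up appointments lists the instruments for phone or video and omits M-VAS. The sanitization paragraph treats the sliding scale as a physical item to be wiped down. All of this favours on-site only, but it remains an inference.

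**Step 4: Table 2.** Five marks survive in the M-VAS row. The table has three on-site columns (2b, 3–12, 13b). If all five marks are genuine, at least 5 − 3 = 2 fall in telehealth columns. Column positions were lost when the PDF was read, so the table cannot show which visits those are. Its visible columns begin at 2a, so it supplies nothing for Visit 1.

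**Step 5: Visit 1 under either reading.** The sentence places M-VAS at on-site visits and Table 2 starts at 2a. The Consent/Screening text says that screening is by video and moves only the physical exam to 2b. None of the three provides a remote M-VAS at Visit 1.

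**The case against.** The strongest reply is that the sentence does not say only, and that Table 2 points the other way. M-VAS is absent from the list of dropped tests, and the same section says that measures tied to the primary aim are kept. A reader might infer that no M-VAS ratings at all exist at Visits 14–17 for remote patients. The documents do not establish that: with five surviving marks against three on-site columns, some telehealth ratings may well be scheduled. This part of the reply stands. What remains is a sentence and a table that, if the marks are genuine, disagree.

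A reader might also infer that the sole back-up for the primary outcome is gone, and the primary analysis with it. That goes too far. M-VAS is the only measure labelled a fail-safe, but the diary continues remotely and the weekly phone contacts include a pain assessment and check diary completion. No rule says how an M-VAS rating would replace diary data, and the mixed model is described as not relying on imputation. Nor do the documents map diary periods B1–B6 to visits, so naming particular diary periods as unprotected would be an assumption.

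Finally, a reader might infer that remote patients enter with no severity check. They do not: the diary NRS criterion is collected remotely, and 2b, before treatment, is an on-site visit at which M-VAS would be rated. The Visit 1 rating nevertheless remains a separate mandatory criterion, joined to the diary one by a conjunction, and it is tied to Visit 1 by name. That gap survives the reply.

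**Conclusion.** The point holds in two parts of different strength. The Visit 1 gap is firm: whichever reading is taken, the documents give no way to obtain M-VAS at a remote screening visit, so that criterion cannot be applied as written. The gap at Visits 14–17 is conditional. If the sentence means on-site only, four of six fail-safe ratings and four of eight secondary-outcome occasions are lost for remote patients. If Table 2 governs, some of these ratings exist and the sentence contradicts its own table. Either way the text needs reconciling.

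The damage falls on a secondary outcome, the designated fail-safe and the documentation of eligibility; the effect on the primary diary analysis is limited. The documents do not state how many patients are handled remotely, so the overall loss cannot be sized. This is worth correcting because the repair is cheap; it is not a demonstrated loss of primary data.

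**What to change.** Reconcile the M-VAS sentence and Table 2 under Assessment Based Visits with the COVID-19 visit list, Section 9 part A, the Hypothesis #1 outcome list and inclusion item 3 in Section 10. Specifically:

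- At telehealth Visits 14–17, have the coordinator ask the same question about average headache since the last visit, answered verbally on a 0–100 numeric scale. This keeps the M-VAS range. Moving to the diary's 0–10 scale would change the scale of an outcome defined as M-VAS.
- Add nothing at 2a or 13a; Visits 2 and 13 are covered by 2b and 13b.
- Record the mode of each rating (device or verbal) and account for it in the M-VAS secondary analysis, for example with a mode term and a sensitivity analysis restricted to device ratings.
- State how the Visit 1 criterion is documented when screening is remote.

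The cost is one question on each of four calls already scheduled, one extra data field, and a short text amendment. The downside is a mode difference between the sliding device and a verbal rating. For a remote patient that difference coincides with the move from the 1-week visit to later follow-up. A shift common to both blinded arms would largely cancel in the between-arm comparison at a given visit, but it would affect change from baseline.
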